RSV	Respiratory Syncytial Virus
SAE	Serious Adverse Event
SAP	Statistical Analysis Plan
SOC	System Organ Class
SRR	Seroresponse rate
ULOQ	Upper Limit of Quantification
YOA	Years of Age

VERSION HISTORY

SAP Version	Approval Date	Protocol Version (Date) on which SAP is Based	Change	Rationale
SAP	12 February 2024	Final: 18 December 2023	Not Applicable	Original version
SAP Amendment 1	19 July 2024	Amendment 1: 03 May 2024	
Updates to align with changes according to protocol amendment: addition of Cohort 3 (addition of Part A or Part B where appropriate, update of Section 4.7.1 and Section 5).
 
Section 4.3.2.1 and 6.3.3.9 (previously 6.2.3.9): Change in tabulation of solicited event duration and number of days with Grade 3 solicited events. Removal of tables for demyelinating disorder AEs.
 
New Section 6.2 following SAP template update.
 
Section 6.3.2.3 (previously
	
The study population has been extended to include a cohort of AIR participants 18-49 YOA to better characterize the safety profile of the RSVPreF3 OA investigational vaccine in this population.
 
Section 4.3.2.1 and 6.3.3.9 (previously 6.2.3.9): Change following project update for the definition of duration of solicited symptoms.
 
Demyelinating disorder AEs will be part of overall AE tables showing different SMQs.

SAP Version	Approval Date	Protocol Version (Date) on which SAP is Based	Change	Rationale
			6.2.2.3): Update on daily recording of solicited events using eDiary.	New Section 6.2 : Definition and analysis of eDiary compliance Section 6.3.2.3 (previously 6.2.2.3): Update following finalization of eDiary and eCRF completion guidelines.
SAP Amendment 2	12 September 2024	Amendment 1: 03 May 2024	Changes for duration analyses (Section 4.3.2.1, 6.3.3.9), Endpoint level compliance (Section 6.2.2) and missing data for solicited events (Section 6.3.2.3)	To account for missing eDiary data as of day 5 onwards, due to non-activation of the eDiary alerts for participants from day 5 onwards in the vendor system. The alerts were re-installed as of 8August2024 onwards.
SAP Amendment 3	04 October 2024	Amendment 1: 03 May 2024	Changes for solicited events analysis (Section 4.3.2.1) and Endpoint level compliance (Section 6.2.2)	To align the solicited events analysis following a request from CBER on study RSV OA=ADJ-017.
SAP Amendment 4	15 Jan 2025	Amendment 1: 03 May 2024	Changes for duration of events (Section 6.3.3.9) and	To include additional analyses on duration of

SAP Version	Approval Date	Protocol Version (Date) on which SAP is Based	Change	Rationale
			Endpoint level compliance (Section 6.2.2)	solicited adverse events and eDiary compliance to account for missing eDiary data as of day 5 onwards, due to non-activation of the eDiary alerts for participants from day 5 onwards in the vendor system.

1. INTRODUCTION

The purpose of this SAP is to describe the planned statistical analyses to be included in the CSR for Study RSV OA=ADJ-025 (222253). Details of the planned interim analyses, as well as the final analyses, are provided.

1.1. Objectives, Estimands and Endpoints

Table 1 Objectives and Endpoints

Objective	Endpoint
Primary* (Part A)	

 To demonstrate the NI** of the humoral immune response in participants 18-49 YOA at increased risk for RSV disease compared to OA (≥ 60 YOA) for the RSV-A strain after RSVPreF3 OA investigational vaccine administration. To demonstrate the NI** of the humoral immune response in participants 18-49 YOA at increased risk for RSV disease compared to OA (≥ 60 YOA) for the RSV-B strain after RSVPreF3 OA investigational vaccine administration. 	
 RSV-A neutralizing titers expressed as GMT ratio (RSV-OA over RSV-A-AIR) at 1 month (Day 31) after study intervention administration*** Seroresponse in RSV-A neutralizing titers from Day 1 to Day 31***. RSV-B neutralizing titers expressed as GMT ratio (RSV-OA over RSV-A-AIR) at 1 month (Day 31) after study intervention administration*** Seroresponse in RSV-B neutralizing titers from Day 1 to Day 31***.
Secondary Safety (Part A and Part B)	

 To evaluate the safety and reactogenicity after the RSVPreF3 OA investigational vaccine administration. 	
 Occurrence of each solicited administration site event with onset within 4 days after dosing (i.e., the day of study intervention administration and 3 subsequent days). Occurrence of each solicited systemic event with onset within 4 days after study intervention administration (i.e., the day of study intervention administration and 3 subsequent days). Occurrence of unsolicited AEs within 30 days after study intervention administration (i.e., the day of study intervention administration and 29 subsequent days). Occurrence of all SAEs (including fatal and related SAEs) and AESIs after study intervention administration (Day 1) up to study end (Month 6).
Secondary Immunogenicity (Part A)	

 To evaluate the humoral immune response to the RSVPreF3 OA investigational vaccine until 6 months after study vaccination for both populations. 	
 RSV-A and RSV-B neutralizing titers, at pre-study intervention administration and 1 month and 6 months after study intervention administration.
Tertiary Immunogenicity (Part A)	
CCI	

AE=Adverse event; AESI=Adverse event of special interest; AIR=At increased risk; CCI=Comorbidity Index; GMT=Geometric mean titer; NI=Non-inferiority; OA=Older adults; RSV=Respiratory syncytial virus; SAE=Serious adverse event; YOA=Years of age.

* Refer to Section [4.2.2](#) for the testing sequence of primary objectives.

** NI criteria are defined in Section [4.2.2](#).

*** Co-primary endpoints. Refer to Section [2](#) for statistical hypotheses.

Primary estimands (for Part A)

The primary question of interest is to evaluate the NI of the humoral immune response after RSVPreF3 OA investigational study intervention in RSV-A-AIR group (18-49 YOA), vaccinated as per protocol when compared to RSV-OA (≥ 60 YOA) group.

Table 2 Primary estimands (Part A)

Treatment	Population	Endpoint (variable)	Attributes		Summary measure
			Intercurrent events (ICEs)	Description	
RSVPreF3 OA investigational vaccine at Day 1.	Non-immunocompromised adults at increased risk for RSV disease with 18-49 YOA. OA with ≥ 60 YOA.	
 • RSV-A neutralizing titers (expressed in ED60) measured at 1 month (Day 31) after study intervention administration. • Seroresponse in RSV-A neutralizing titers (expressed in ED60) from Day 1 to Day 31. • RSV-B neutralizing titers (expressed in ED60) measured at 1 month (Day 31) after study intervention administration. • Seroresponse in RSV-B neutralizing titers (expressed in ED60) from Day 1 to Day 31. 	Taking prohibited medication /vaccine or intercurrent medical condition prior to Day 31.	Data collected after ICEs will be excluded from the analysis at Day 31 (Hypothetical strategy). Rationale: To evaluate the immunogenicity parameters in the absence of ICE.	Ratio of GMTs with 95% CI and difference in seroresponse rate (SRR) with 95% CI for RSV-A and RSV-B neutralizing titers (ED60) at Day 31 between the RSV-OA group (≥ 60 YOA) and the RSV-A-AIR group (18-49 YOA).

SRR is defined as the proportion of participants having a fold increase in neutralizing titers (1-month post-study intervention administration over pre-study intervention administration) ≥ 4 .

AIR=At increased risk; CI=Confidence interval; ED60= Estimated dilution 60; GMT=Geometric mean titer; OA=Older adults; YOA=Years of age

Rationale for estimand: The primary estimands address the objective of demonstrating the NI of the humoral immune response in non-immunocompromised adults aged 18-49 YOA AIR for RSV disease, when compared to older adults aged ≥ 60 YOA after administration of a single dose of RSVPreF3 OA investigational vaccine. This is done by estimating the true effect of the vaccine without any confounding of other medications/vaccinations/medical condition(s) on the target population since the impact of developing medical condition(s) forbidden by protocol and use of forbidden medications and vaccinations is anticipated to modify the vaccine effect.

[figure not shown]
Secondary estimands (for Part A and Part B)

Table 3 Secondary estimands for safety (Part A and Part B)

Treatment	Population	Endpoint (Variable)	Attributes		Summary measure	
			Intercurrent events (ICEs)			
			Description	Handling strategy		
RSVPreF3 OA investigational vaccine at Day 1.	Non-immunocompromised adults at increased risk for RSV disease with 18-49 YOA. OA with ≥ 60 YOA.	
 Occurrence of each solicited administration site event with onset within 4 days after study intervention administration. Occurrence of each solicited systemic event with onset within 4 days after study intervention administration. Occurrence of unsolicited AEs within 30 days after study intervention administration. Occurrence of SAEs (including fatal and related SAEs) and AESIs after study intervention administration (Day 1) up to study end (Month 6). 	Taking prohibited medication /vaccine or intercurrent medical condition during respective duration.	All the data collected for the variable of interest are used regardless of whether the intercurrent event occurs (treatment policy).	The percentage of participants by group who report each of the endpoints.	

AE=Adverse event; AESI=Adverse event of special interest; RSV=Respiratory syncytial virus; SAE=Serious adverse event; YOA=Years of age.

1.2. Study Design

Overview of Study Design and Key Features		
Interval	Planned visit interval	Allowed interval range
Visit 1→Visit 2	30 days	30-42 days
Visit 1→Visit 3 (Part A)	180 days	180-210 days
Visit 1→ Contact (Month 6) (Part B)	180 days	180-210 days

If the study intervention date is different from the ICF signature date, the study intervention date needs to be taken as a reference for calculating intervals relative to subsequent visits.
 
Interval is computed as the difference between 2 dates.
		
Design Features	
Phase 3b, open-label, uncontrolled (as there is no comparative intervention), non-randomized study. The study will be conducted in 2 Parts – Part A and Part B. Part A will include 2 parallel cohorts (Cohort 1 and Cohort 2) and Part B will include 1 cohort (Cohort 3).
 
Duration of the study: Approximately 6 months for all participants.
	
Study intervention	Participants will receive 1 dose of RSVPreF3 OA investigational vaccine at Visit 1 (Day 1).	
Study intervention Assignment	
Participants will be enrolled into 3 different cohorts.
 
Part A:
 
Cohort 1: Participants 18-49 YOA at increased risk for RSV disease will be enrolled into Cohort 1 in 3 disease categories (cardiopulmonary conditions, diabetes mellitus and other disease categories), with approximately 25% of participants with cardiopulmonary conditions and approximately 25% of participants with diabetes mellitus. The remaining approximately 50% can be distributed freely across the above 2 disease categories as well as include participants with chronic renal or liver disease or neurological or neuromuscular disease.
 
Cohort 2: Participants \geq60 YOA will be enrolled into Cohort 2 in 2 age categories (60-69 YOA and \geq 70 YOA), with approximately 40% of participants 60-69 YOA and approximately 30% of participants \geq 70 YOA. The remaining 30% can be distributed freely across the 2 age categories.
 
Part B:
 
Cohort 3: Participants 18-49 YOA at increased risk for RSV disease will be enrolled into Cohort 3 in 3 disease categories (cardiopulmonary conditions, diabetes mellitus and other disease categories), with approximately 25% of participants with cardiopulmonary conditions and approximately 25% of participants with diabetes mellitus. The remaining approximately 50% can be distributed freely across the above 2 disease categories as well as include participants with chronic renal or liver disease or neurological or neuromuscular disease.
 
In addition, enrolment rules will be applied to ensure adequate representation by sex category within all 3 Cohorts, with approximately 35% of male participants per cohort and approximately 35% of female participants per cohort. The remaining 30% can be distributed freely across the 2 categories.
 
Participants contributing to the CCI [REDACTED] (only Part A) will be recruited from a selected number of countries and selected number of clinical sites. In the selected sites, the investigator will allocate if possible, at Visit 1, the first participants in each group to the CCI [REDACTED] until the allocated target is reached.
	
Day 31 Analysis (Part A)	A first analysis will be performed on all immunogenicity, reactogenicity and safety data available and as clean as possible, when data for at least primary and secondary endpoints up to Visit 2 (Day 31) are available for all participants in Part A. This analysis will be considered as final for the primary endpoints	
Month 6 Analysis (Part A)	An optional and separate analysis may be performed when safety data up to Month 6 are available for all participants in Part A, if required.	

Overview of Study Design and Key Features	
Day 31 Analysis (Part B)	An optional and separate analysis may be performed when safety data up to Visit 2 (Day 31) are available for all participants in Part B, if required. This analysis may be combined with Month 6 analysis for Part A.
Month 6 Analysis (Part A)	An optional and separate analysis may be performed when immunogenicity data up to study conclusion (Visit 3, Month 6) are available for all participants in Part A, if required.
End-of-study Analysis	An end of study analysis will be performed when all data for secondary endpoints up to study conclusion (Visit 3/Contact, Month 6) will be available for all participants

2. STATISTICAL HYPOTHESES

Statistical hypotheses are associated to the confirmatory primary NI objectives, which will be tested according to the hierarchical testing procedure described in Section 2.1. Global type I error is controlled at 2.5% (1-sided).

Table 4 Study objectives and null hypothesis

Objectives	Null hypothesis
Primary (Part A)	

 To demonstrate the NI of the humoral immune response in participants 18-49 YOA at increased risk for RSV disease compared to OA (≥ 60 YOA) for the RSV-A strain after RSVPreF3 OA investigational vaccine administration. 	
 Null hypothesis 1 (H1): The anti-RSV-A GMT ratio RSV-OA (≥ 60 YOA) over RSV-A-AIR (18-49 YOA) is >1.5 or the SRR difference (RSV-OA [≥ 60 YOA] minus RSV-A-AIR [18-49 YOA]) is $>10\%$ at 1 month post RSVPreF3 OA vaccine administration. This must be rejected in favor of the alternative hypothesis that the GMT ratio is ≤ 1.5 and the SRR difference is $\leq 10\%$.

 To demonstrate the NI of the humoral immune response in participants 18-49 YOA at increased risk for RSV disease compared to OA (≥ 60 YOA) for the RSV-B strain after RSVPreF3 OA investigational vaccine administration. 	
 Null hypothesis 2 (H2): The anti-RSV-B GMT ratio RSV-OA (≥ 60 YOA) over RSV-A-AIR (18-49 YOA) is >1.5 or the SRR difference (RSV-OA [≥ 60 YOA] minus RSV-A-AIR [18-49 YOA]) is $>10\%$ at 1 month post RSVPreF3 OA vaccine administration. This must be rejected in favor of the alternative hypothesis that the GMT ratio is ≤ 1.5 and the SRR difference is $\leq 10\%$.

A=Adults; AIR=At increased risk; GMT=Geometric mean titer; H1=Null hypothesis 1; H2=Null hypothesis 2; NI=Non-inferiority; OA=Older adults; RSV=Respiratory syncytial virus; SRR=Seroresponse rate; YOA=Years of age.

2.1. Multiplicity Adjustment

In order to control the global type I error at 2.5% (1-sided), the primary objectives will be assessed using a hierarchical testing. NI will be first tested for RSV-A strain and, only if NI has been demonstrated, will the NI be tested for RSV-B strain.

3. ANALYSIS SETS

Analysis Set	Definition / Criteria	Analyses Evaluated
Screened Set	All participants who were screened for eligibility.	Study Population
Enrolled Set	All participants who entered the study (who were allocated a treatment number or received study intervention or underwent a post screening study procedure). Note: screening failures (who never passed screening) and participants screened (met eligibility) but never enrolled into the study are excluded from the Enrolled analysis set as they did not enter the study.	Study Population
Exposed Set (ES)	All participants who received the study intervention. Analysis per group is based on age and medical condition (adults 18-49 YOA at increased risk for RSV disease versus older adults ≥ 60 YOA).	Study population, Reactogenicity, Safety
Per-Protocol Set (PPS)*	All eligible participants who received the study intervention as per protocol, had immunogenicity results pre- and post-dose, complied with blood draw intervals, without intercurrent conditions that may interfere with immunogenicity and without prohibited concomitant medication/vaccination. Analysis per group is based on age and medical condition (adults 18-49 YOA at increased risk for RSV disease versus older adults ≥ 60 YOA).	Immunogenicity

*Contribution of participants to PPS will be defined by timepoint

3.1. Criteria for eliminating data from Analysis Sets

Elimination codes will be used to identify participants to be eliminated from analysis. Details are provided below for the Enrolled Set, the Exposed Set (ES) and the Per Protocol Set (PPS).

3.1.1. Elimination from Enrolled Set

The following codes will be used for identifying participants to be eliminated from the Enrolled Set:

- Code 800 (Fraudulent data)
- Code 900 (Invalid informed consent)

3.1.2. Elimination from ES

The following codes will be used for identifying participants to be eliminated from the ES:

- Code 800 (Fraudulent data)
- Code 900 (Invalid informed consent)
- Code 1030 (Study intervention not administered at all)

3.1.3. Elimination from PPS

A participant will be excluded from the populations for analysis under the following conditions:

- For codes 800, 900, 1030, 1070, 1080, 1090 and 2010: participants will be eliminated for all visits.
- For codes 1040, 2040 and 2050: participants will be eliminated from a specific visit (at which the condition is met) onwards.
- For codes 2020 (2020h and 2020c for humoral and **CCI** respectively), 2090 (2090h and 2090c for humoral and **CCI** respectively), 2100 (2100h and 2100c for humoral and **CCI** respectively), 2120: participants will be eliminated at the specific visit at which the condition is met.

Table 5 List of elimination codes

Code	Condition under which the code is used	Visit / Contact (timepoints) where the code is checked	Visit from when it is applicable	Applicable for analysis set/endpoint
800	Fraudulent data	All	All	Enrolled Set, ES, PPS
900	Invalid informed consent	All	All	Enrolled Set, ES, PPS
1030	Study intervention not administered at all	Visit 1	All	ES, PPS
1040	Administration of concomitant vaccine(s) forbidden in the protocol (as defined in Section 5.2.2 of protocol)	All	From the specific visit the condition is met	PPS
1070	Vaccine administration not according to protocol: 
 • Participant was vaccinated with the correct vaccine but containing a lower volume • Wrong replacement or study vaccine administered (not compatible with the vaccine regimen associated to the treatment number) • Route of the study vaccine is not intramuscular • Wrong reconstitution of administered vaccine 	Visit 1	All	PPS
1080	
 • Vaccine administration after a temperature deviation • Vaccine administered despite a Good Manufacturing Practices (GMP) no-go temperature deviation 	Visit 1	All	PPS
1090	Vaccine administration after expiration	Visit 1	All	PPS
2010	Protocol deviation linked to inclusion/exclusion criteria	All	All	PPS

Code	Condition under which the code is used	Visit / Contact (timepoints) where the code is checked	Visit from when it is applicable	Applicable for analysis set/endpoint
2020	All Pre-dose results are missing	Visit 1	At the specific visit the condition is met	PPS
2040	Administration of any medication forbidden by the protocol (as defined in Section 5.2.2 of protocol)	All	From the specific visit the condition is met.	PPS
2050	Intercurrent medical condition: Participants may be eliminated from the PPS for immunogenicity if, during the study, they incur a condition that has the capability of altering their immune response or are confirmed to have an alteration of their initial immune status.	All	From the specific visit the condition is met.	PPS
2090	Participants did not comply with blood sample schedule: 
 Number of days between vaccination (Visit 1) and blood sample (Visit 2) is outside [30-42] days. Number of days between vaccination (Visit 1) and blood sample (Visit 3) is outside [180-210] days. 	Visit 2, Visit 3	At the specific visit the condition is met	PPS
2100	Immunological results not available post-vaccination	Visit 2, Visit 3	At the specific visit the condition is met	PPS
2120	Obvious incoherence/abnormality or error in laboratory data 
 Unreliable released data as a result of confirmed sample mismatch or confirmed inappropriate sample handling at laboratory. 	All	At the specific visit the condition is met	PPS

4. STATISTICAL ANALYSES

4.1. General Considerations

4.1.1. General Methodology

- For the purpose of immunogenicity analyses, any missing or non-evaluable immunogenicity measurement will not be replaced. The descriptive analysis performed for each assay at each time point will exclude participants with a missing or non-evaluable measurement.

- Titers below the assay cut-off (LLOQ) will be replaced by half the assay cut-off (LLOQ/2) and titers above the upper limit of quantification (ULOQ) will be replaced by the ULOQ to compute GMTs, SRRs and MGIs. For the display of reverse cumulative curve, titers below LLOQ and above ULOQ won't be replaced.
- Confidence intervals (CIs) will use 95% confidence level. 95% CIs for GMT and MGI will be based on a back transformation of CI for the mean of \log_{10} -transformed values. Exact 95% CIs around proportions are derived using the method of Clopper and Pearson [[Clopper](#), 1934]. 95% CI for group difference in proportion will be based on Miettinen and Nurminen confidence interval [[Miettinen](#), 1985].
- Unless otherwise specified, continuous data will be summarized using descriptive statistics: n, mean, standard deviation, median, minimum, and maximum. Categorical data will be summarized as the number and percentage of participants in each category.
- Seroresponse rate (SRR) is defined as the proportion of participants having a fold increase in neutralizing titers (post-study intervention administration over pre-study intervention administration) ≥ 4 .
- The mean geometric increase (MGI) is defined as the geometric mean of the within-participant ratios of the post-vaccination titer over pre-vaccination (Visit 1, Day 1).

4.1.2. Baseline Definition

For all endpoints the baseline value will be the latest pre-dose assessment with a non-missing value, i.e., the assessment at Visit 1 (Day 1).

Unless otherwise stated, if baseline data is missing no derivation will be performed and baseline will be set to missing.

4.2. Primary Endpoints Analyses (Part A)

4.2.1. Definition of endpoints/estimands

Refer to Section [1.1](#) for the definition of primary immunogenicity (humoral response) endpoints/estimands.

4.2.2. Main analytical approach

Primary estimand analysis will be performed on the Per-Protocol Set (PPS) for participants in Part A. If, in any group, the percentage of vaccinated participants with serological results excluded from the PPS is more than 5%, a second analysis based on the ES will be performed to complement the PPS analysis.

RSV-A and RSV-B neutralizing group GMT ratio at 1 month after the RSVPreF3 OA vaccine administration will be computed for RSV-OA (≥ 60 YOA) cohort over RSV-A-AIR (18-49 YOA) cohort, with 95% CI, using an CCI on log10-transformed titers for each neutralization assay. The model will include the group (RSV-OA (≥ 60 YOA) and RSV-A-AIR (18-49 YOA)) and the baseline log10-transformed titer as covariate.

RSV-A and RSV-B neutralizing group SRR differences at 1 month after the RSVPreF3 OA vaccine administration will be computed for RSV-OA (≥ 60 YOA) cohort minus RSV-A-AIR (18-49 YOA) cohort, with 95% CI. The 95% CI will be derived using the method of CCI

Missing data will not be imputed.

Success criteria for NI:

- In order to control the global type I error at 2.5% (1-sided), the primary objectives will be assessed using a hierarchical testing. NI will be first tested for RSV-A strain and, only if NI has been demonstrated, will the NI be tested for RSV-B strain.
- NI for RSV-A strain will be claimed to be successful if the upper limit of the 95% CI for the RSV-A neutralizing group GMT ratio will be ≤ 1.5 and the upper limit of 95% CI for the RSV-A neutralizing group SRR difference will be $\leq 10\%$.
- NI for RSV-B strain will be claimed to be successful if NI has been demonstrated for RSV-A strain and if the upper limit of the 95% CI for the RSV-B neutralizing group GMT ratio will be ≤ 1.5 and the upper limit of 95% CI for the RSV-B neutralizing group SRR difference will be $\leq 10\%$.

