4.2. Scientific rationale for study design

RSV is a respiratory infection which may lead to an increased risk for RSV disease in OA and adults AIR for RSV disease. The efficacy of a single dose of the RSVPreF3 OA investigational vaccine in the prevention of RSV disease in OA \geq 60 YOA has been established in the Phase 3 clinical study RSV OA=ADJ-006 (refer to IB).

The immune response of AIR patients has been shown to be non-inferior in patients aged 50-59 compared to the OA population as of 60 YOA. Part A of this study aims to continue exploring the immune response of patients considered AIR between the ages of 18-49. By including a cohort of OA with the same inclusion and exclusion criteria as in the pivotal RSV OA=ADJ-006 efficacy study in this study, vaccine efficacy can potentially be inferred based on NI of the immune response.

CCI

Lastly, safety of the RSVPreF3 OA investigational vaccine will be evaluated in Part A and Part B of the study. By including Part B, safety will be evaluated in a larger sample size of adults AIR aged between 18-49, which will allow better characterization of the safety profile of the RSVPreF3 OA investigational vaccine in this population.

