4.3.2.2.1. Between groups assessment

Considering the sampling timepoint at 1-month post-study intervention administration, same analysis as for primary endpoint (refer to Section 4.2.2) will be performed using **CCI** unit for computation of the GMT ratio and SRR difference.

Considering the sampling timepoint at 6-month post-study intervention administration, the following analysis will be performed:

- The 95% CIs for group GMT ratios (RSV-OA (≥ 60 YOA) cohort over RSV-A-AIR (18-49 YOA) cohort) will be derived from an ANCOVA model on \log_{10} -transformed titers for each neutralization assay. The model will include the group and the baseline \log_{10} -transformed titer as covariate. The group GMT ratios will be based on a back transformation of group contrast in the ANCOVA model applied to the logarithmically transformed titers.
- The 95% CIs for group SRR difference (RSV-OA (≥ 60 YOA) cohort minus RSV-A-AIR (18-49 YOA) cohort)
- Results will be reported using both ED60 and **CCI** units.

All between groups analyses of secondary endpoints presented in this section will be descriptive with the aim to characterize the difference in immunogenicity between groups. These descriptive analyses should be interpreted with caution considering that there is no adjustment for multiplicity for these comparisons.

4.3.2.2.2. *Within groups assessment*

For each timepoint with blood sample collection for humoral immune response and for RSV-A/B neutralizing titers, the following analysis will be performed by group:

- a. Percentage of participants with neutralizing titers equal to or above pre-defined assay cut-offs and their 2-sided 95% CIs will be tabulated.
- b. SRR and 95% CI will be tabulated.
- c. Unadjusted GMTs and their 95% CIs will be tabulated and displayed graphically.
- d. The kinetics of unadjusted GMTs will be plotted as a function of time for participants with results available at all timepoints.
- e. MGIs and their 95% CIs will be tabulated.
- f. Distribution of neutralizing titers will be displayed using reverse cumulative curves.
- g. Results will be reported using both ED60 and CCI units.

[figure not shown]
4.3.3. *Additional considerations*

4.3.3.1. *Atrial Fibrillation (AF) AESIs*

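### Does the seroresponse co-primary need a baseline-adjusted supportive analysis because the GMT co-primary is adjusted for Day 1 titer and the cohorts are not randomised?

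*SAP*

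**What the plan says.** SAP 4.2.2, like Protocol 9.3.1, treats the two co-primaries differently. The model for the Day 31 GMT ratio contains group and "the baseline log10-transformed titer as covariate". For SRR the text is "RSV-A and RSV-B neutralizing group SRR differences at 1 month after the RSVPreF3 OA vaccine administration will be computed for RSV-OA" minus RSV-A-AIR, with a 95% CI and no covariate, stratum or model. The interval method is masked there, but SAP 4.1.1 gives it: "95% CI for group difference in proportion will be based on Miettinen and Nurminen confidence interval". The power footnote in SAP Section 5 uses the same method.

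Seroresponse is a rise of at least 4-fold from Day 1 to Day 31 within the participant (Protocol Table 7, SAP 4.1.1). Both co-primaries must meet their margins, 1.5 for the GMT ratio and 10 points for SRR, before a strain succeeds.

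The other readable SRR analyses are also unadjusted:
- the conditional repeat in 4.2.2, "a second analysis based on the ES will be performed to complement the PPS analysis";
- the Day 31 repeat in another unit and the Month 6 comparison in 4.3.2.2.1, "The 95% CIs for group SRR difference";
- the within-group tables in 4.3.2.2.2 and the tables by age in 4.6.1.1.

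The within-group section also plans, at each blood-sampling timepoint and so including Day 1, "Unadjusted GMTs and their 95% CIs will be tabulated and displayed graphically", together with reverse cumulative curves. Mean geometric increases by group are planned as well.

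**The concern.** The cohorts are non-randomised and defined by age and medical condition, so nothing in the design makes their Day 1 titers alike. Having the Day 1 titer as the denominator of the fold rise does not remove its influence. If the slope of log10 Day 31 titer on log10 Day 1 titer is below 1, participants who start higher are less likely to reach a 4-fold rise, and a baseline gap between cohorts enters the SRR difference.

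SRR is also the co-primary with less power (93.08% and 90.44%, against 99.95% for GMT), so a few points could decide the result. Protocol 4.2 states the stake: "vaccine efficacy can potentially be inferred based on NI of the immune response". A higher baseline in the younger cohort could make SRR fail although response given baseline is equal. A lower one would help SRR pass. An adjusted SRR difference would lose no participants, since the Per-Protocol Set already consists of those who "had immunogenicity results pre- and post-dose".

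**Working it through.** **1. The plan's own figures.** Inputs from Protocol Table 20 and SAP Table 6: 361 evaluable per cohort, SRR 81.6% (RSV-A) and 78.7% (RSV-B) taken as equal in both cohorts, margin 10 points, one-sided 2.5%, SD 0.45 on log10.
- Full enumeration of the Miettinen-Nurminen test gives power 93.2% and 90.6% (stated 93.08% and 90.44%).
- GMT: SE = 0.45 × √(2/361) = 0.0335. The non-central t test with margin 0.176 gives 99.95%, as stated.
- Type I error at a crude difference of exactly 10 points: 2.51% (81.6 v 71.6) and 2.50% (78.7 v 68.7).

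The test is therefore valid for the quantity named in the hypotheses.

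**2. How far a baseline gap could move SRR.** The documents give no Day 1 titers. Assumed: bivariate normal log10 titers, Day 31 SD 0.45 (Table 20 does not say that its SD is post-dose), baseline SD (SDb) 0.35 to 0.45, correlation r 0.3 to 0.7, and identical response given baseline.
- slope = r × 0.45/SDb
- fold-rise SD = √(0.45² + SDb² − 2 × r × 0.45 × SDb)
- d = (1 − slope) × gap / fold-rise SD
- younger-cohort SRR = Φ(z − d), with z = 0.900 for 81.6%

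RSV-A, younger cohort 0.10 log10 higher:
- SDb 0.45, r 0.3: slope 0.30, fold-rise SD 0.532, d = 0.70 × 0.10/0.532 = 0.131. SRR = Φ(0.769) = 77.9%, a shift of 3.7 points; power 56%.
- SDb 0.35, r 0.7: slope 0.90, fold-rise SD 0.323, d = 0.10 × 0.10/0.323 = 0.031. SRR = 80.8%, a shift of 0.8 points; power 88%.

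For RSV-B the shift is 0.9 to 4.0 points and power 48 to 84%. With the gap reversed, the shifts are −0.8 to −3.3 (RSV-A) and −0.9 to −3.6 (RSV-B). The mechanism is real, but its size and direction here are unknown.

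**3. What the plan would already show.** In these scenarios the true adjusted GMT ratio is 1. Its SE is 0.45 × √(1 − r²) × √(2/361), that is 0.0320 at r = 0.3 and 0.0239 at r = 0.7. The 95% half-widths are 0.0627 and 0.0470 on log10, or factors of 1.16 and 1.11, against a margin of 1.5. A missed SRR margin beside an adjusted ratio near 1 and visibly different Day 1 GMTs can be read as a baseline effect.

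**4. What an adjusted SRR difference would add.** In simulation, a logistic model standardised to the pooled baseline gave means between −0.12 and +0.13 points when response given baseline was identical. That is the condition such a model assumes.

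Now suppose instead that the two fold-rise distributions are identical, which is equality on the trial's own definition of seroresponse. The crude difference is 0. Standardised to the pooled baseline, the difference is ½ × [Φ(z − d) − Φ(z + d)] for a higher baseline in the younger cohort:
- RSV-A, d = 0.131: ½ × (77.9 − 84.9) = −3.5 points.
- RSV-A, d = 0.031: ½ × (80.8 − 82.4) = −0.8 points.
- RSV-B (z = 0.796), d = 0.131: ½ × (74.7 − 82.3) = −3.8 points.

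The signs reverse for a lower baseline. Simulation of the logistic model for RSV-A agrees: −0.9 to −3.6 at +0.10 and +0.6 to +3.5 at −0.10. The adjusted estimate can thus show a difference of the same order as the shift it is meant to explain.

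**The case for a change.** The strongest counter-argument is that the SAP itself finds Day 1 titer worth adjusting for in the GMT ratio, at Day 31 and again at Month 6, and gives no matching view for SRR. Day 1 tables would reveal a gap but not how many SRR points it accounts for. One descriptive model per strain is cheap and needs no new data.

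Part of this stands. No readable SRR analysis adjusts for baseline, and attribution in percentage points is not available from the planned tables. Nor does the GMT criterion fully neutralise a favourable baseline gap. With the half-widths above, an observed adjusted ratio up to about 1.5/1.16 = 1.29 or 1.5/1.11 = 1.35 would still pass.

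That does not amount to a flaw. The GMT endpoint is the Day 31 titer alone, so baseline can enter only through the model. Seroresponse is defined relative to Day 1, and its crude difference is a legitimate comparison of two populations as they are. Standardising to the pooled baseline describes a mixture that is neither cohort. In non-randomised cohorts, which estimate is the more informative depends on whether equality means equal response given baseline or equal fold rise, an assumption that cannot be tested. Where the two estimates disagreed, there would be no rule for reading them.

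**Conclusion.** The concern does not hold. Estimand, hypotheses, test and power agree on the crude SRR difference, the test keeps its level, and the stated power reproduces. A baseline-adjusted SRR difference would alter no test, margin, power or non-inferiority decision, and it would not recover any power lost to a baseline gap. The main interpretive risk, mistaking a baseline gap for a weaker response, is largely covered by the required adjusted GMT ratio read with the Day 1 summaries by group. What is left is attribution in percentage points, 0.8 to 4.0 for a gap of +0.10 log10, where the gap, the baseline SD and the correlation are all assumed.

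The conclusion rests on the readable text. SAP 4.4 and the text after 4.6.1.1 are masked, so whether such an analysis exists there cannot be checked. It also accepts the marginal SRR difference as the quantity of interest, as the protocol does.
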